#### **4.2.5 Removal of Subjects from Study**

In accordance with the Declaration of Helsinki and the Code of Federal Regulations, a subject has the right to withdraw from the study at any time for any reason without prejudice to his/her future medical care by the physician or the institution. Should a subject (or subject's legally authorized guardian/representative) decide to withdraw, all efforts will be made to collect and report the final visit observations as thoroughly and timely as possible.

The primary reason for early termination and the date of termination will be recorded in the electronic case report form. Reasons may include:

##### **Investigator Decision**

If the subject experiences an adverse event or the Principal Investigator or Medical Monitor believes it is in their best interest to discontinue participation in the study for other reasons, they

will be withdrawn from the study.

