### **Secondary:**

1. Change in radiographic angular/positional alignment before and after the Lapiplasty® Procedure [Time Frame: pre-operatively, 6 weeks, 4 months, 6 months, 12 months, and 24 months, post-Lapiplasty® Procedure].
2. Evaluate clinical/radiographic healing (union vs non-union). Non-union defined as lucency at TMT joint, hardware failure and/or loss of correction (recurrence), plus clinical pain at first TMT joint at 12 months post- Lapiplasty® Procedure.
3. Clinical complications through 24-month follow-up visit due to the Lapiplasty® System Implants, the Lapiplasty® Procedure, the post-operative weight-bearing protocol or health conditions that could affect other outcome measures.
4. Time to start weight-bearing in a boot, in days.
5. Time to start weight-bearing in shoes, in days.

6. Time to return to full unrestricted activity, in days.
7. Change in pain at the base of the big toe (bunion related) assessed via a Visual Analog Scale (VAS) at 0-14 days, 14-21 days, 6 weeks, 4 months, 6 months, 12 months and 24 months post-Lapiplasty® Procedure, in comparison to baseline visit pain.
8. Change in Quality of Life, (PROMIS-29, PROMIS-25 and MOxFQ) defined as the total score measured at 6 months, 12 months and 24 months post-Lapiplasty® Procedure, in comparison to baseline visit.
9. Change in Range of Motion - 1st MTP dorsiflexion and plantarflexion at 12 months and 24 months post-Lapiplasty® Procedure, in comparison to baseline visit.
10. Change, if any, in initial incision length during Lapiplasty® Procedure.
11. Change in radiographic foot length and width at 12 months post-Lapiplasty® Procedure in comparison to baseline visit.
12. Change in swelling at 6 weeks and 4 months post-Lapiplasty® Procedure as compared to 0-2 week visit.
13. Change in scar quality at 4 months, 6 months, and 12 months post-Lapiplasty® Procedure in comparison to baseline visit.
14. Correlation between amount of time external positioner is actively used during Lapiplasty Procedure with necrosis, blistering, bruising and tissue ulceration events.

[figure not shown]

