### **9.3 Analysis Population**

Intent-to-Treat (ITT) population: The ITT population is defined as all enrolled subjects who were treated with the Lapiplasty® Procedure using the Mini-Incision™ System.

Per-Protocol (PP) Population: The per-protocol population is defined as all enrolled subjects who were treated with the Lapiplasty® Procedure using the Mini-Incision™ System who did not experience a major protocol violation. Major protocol violations include, but are not limited to, subjects who:

- Entered the study although they did not satisfy the eligibility criteria;
- Completed incorrect version of PROMIS based on age of subject;
- Did not return to protective weight-bearing activities by 3 weeks (+3 days);
- Received Lapiplasty® Procedure (or other hallux valgus procedures) on contralateral foot less than 6 months after initial index procedure; or
- Developed withdrawal criteria during the study but were not removed from study participation.

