## **10.1 Adverse Events**

### **10.1.1 Definition of an Adverse Event**

Adverse Event (AE): any undesirable clinical occurrence or change from a patient's baseline (pre-index procedure) condition, whether it is device related or not.

Adverse Event Identification: a condition that is one of the following:

- a. A unique symptom or event that is a change from the subject's baseline status
- b. A series of symptoms or events that can be categorized as a single entity
- c. A specific diagnosis responsible for a clinical change
- d. A worsening or exacerbation of a pre-existing condition

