All Serious Adverse Events that are related to the index procedure or the Lapiplasty® devices must be reported by the Investigator by submitting the AE eCRF to TMC within 10 days of becoming aware of

the AE and recorded on the Serious Adverse Event Source Document Collection Form. Any event determined by the Investigator to be life threatening or to have led to death should be reported within 24 hours.

The Investigator shall send a written report including a narrative description of the SAE to TMC within three (3) working days of the initial report. The Investigator should follow all unresolved SAEs until the events are resolved, or the subject has exited the study, or the AE is otherwise explained.

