6.2.2 Per-Protocol Population

The Per-Protocol (PP) population is defined as the ITT population who did not experience a major protocol violation. Major protocol violations include, but are not limited to, subjects who:

- Entered the study although they did not satisfy the eligibility criteria
- Completed incorrect version of PROMIS based on age of subject
- Did not return to protective weight-bearing activities by 3 weeks (+3 days)
- Received Lapiplasty® Procedure (or other hallux valgus procedures) on contralateral foot less than 6 months after initial index procedure
- Developed withdrawal criteria during the study, but were not removed from study participation

All effectiveness, safety, and health economic outcomes analyses will utilize the ITT population. If the PP population and ITT population differ considerably, sensitivity analyses will be performed using the PP population.

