7.1.2 Protocol Deviations

Protocol deviations are events occurring during the conduct of the study which are not in compliance with the protocol and for which an amendment has not been granted. Protocol deviations affecting the scientific soundness of the study or the rights, safety, or welfare of the subjects, will be reported by the principal investigator (PI), as required by the Institutional Review Board (IRB). Protocol deviations will be summarized and grouped into relevant categories for analysis and may include, but not be limited to, subjects who:

- Entered the study although they did not satisfy the eligibility criteria
- Completed incorrect version of PROMIS based on age of subject
- Did not return to protective weight-bearing activities by 3 weeks (+3 days)
- Received Lapiplasty® Procedure (or other hallux valgus procedures) on contralateral foot less than 6 months after initial Index Procedure
- Developed withdrawal criteria during the study, but were not removed from study participation

A subject for whom at least one of the aforementioned deviations is reported may be excluded from the PP population.

Minor protocol deviations will be listed by site, subject, and visit within subject.

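### Protocol 4.2.5, as worded, withdraws any subject who has an adverse event from the study, which contradicts the 24-month follow-up of complications in the rest of the plan

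*Protocol*

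**What the plan says.** Protocol 4.2.5 lists possible reasons for early termination. Under Investigator Decision the condition is "If the subject experiences an adverse event or the Principal Investigator or Medical Monitor believes it is in their best interest to discontinue participation" for other reasons, and the consequence is that the subject "will be withdrawn from the study". Protocol 10.1.1 defines an adverse event as "any undesirable clinical occurrence or change from a patient's baseline (pre-index procedure) condition, whether it is device related or not".

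Protocol 9.3 includes among major protocol violations subjects who "Developed withdrawal criteria during the study but were not removed from study participation". SAP 6.2.2 has the same bullet ("Developed withdrawal criteria during the study, but were not removed from study participation") and defines the per-protocol (PP) set as ITT without a major violation. Protocol 8.2.2 and SAP 7.1.2 repeat the bullet in their deviation lists. SAP 7.1.2 is softer on the result: "A subject for whom at least one of the aforementioned deviations is reported may be excluded from the PP population".

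Elsewhere the plan expects these subjects to remain. Secondary endpoint 3 is "Clinical complications through 24-month follow-up visit due to the Lapiplasty® System Implants" and related causes. On serious events, Protocol 10.2.4 says "The Investigator should follow all unresolved SAEs until the events are resolved, or the subject has exited the study".

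**The concern.** The adverse-event limb of the sentence stands by itself before the first *or*. It carries no threshold of severity, relatedness or judgement, and its consequence is mandatory. The study intervention is one operation, already finished when nearly all adverse events will arise. Withdrawal from the study therefore cannot reduce exposure; it only stops data collection.

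At stake are the 24-month recurrence estimate and the record of later complications and repeat surgery in subjects who have already had a problem. A second matter is the composition of the PP set, which the SAP names as the sensitivity check on the primary endpoint.

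**Working it through.** This is mainly a check of text against text. There is no design figure to reproduce, because both documents state that the 200 subjects do not come from a formal calculation.

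**Step 1: how far the trigger reaches.** Under Protocol 10.1.1 relatedness is irrelevant. Protocol 10.2.4 goes further: it classes expected post-operative pain, minor swelling and temporary numbness as adverse events that are simply not entered on the eCRF. Applied literally, the 4.2.5 sentence would reach almost every operated subject, so sites cannot carry it out as written.

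**Step 2: provisions that assume subjects with an adverse event stay in.**

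| Place | Provision |
|---|---|
| Schedule of Assessments | Adverse events and secondary surgery assessed through Visit 9 (24 months) |
| Protocol 3.0, secondary endpoint 3 | Complications counted to 24 months |
| Protocol 4.1 | Follow-up of up to two years, for complications among other outcomes |
| Protocol 7.10 | Unscheduled visits for complications |
| Protocol 10.2.4 | Continued follow-up of unresolved serious events |
| SAP 7.3.1 | Events leading to discontinuation summarised separately from all events |

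None of these fits withdrawal on any adverse event.

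**Step 3: what each course of action does to the data.**

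- *Subject withdrawn.* The 4.2.5 commitment to obtain final-visit observations is written for subjects who themselves decide to leave. Study Exit (7.11) collects a date and a reason. The duty to follow a serious event can end at exit. Efficacy and health-economic values are not imputed (Protocol 9.5, SAP 6.3). The subject is nominally ITT but has no 24-month radiograph, and so drops out of the numerator and denominator of the primary result.
- *Subject kept in.* The subject stays in every ITT analysis but meets the withdrawal-criteria bullet. Protocol 9.3 and SAP 6.2.2 then put the subject outside PP; SAP 7.1.2 makes this discretionary.

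**Step 4: illustration of size.** The documents give neither an adverse-event rate nor a failure rate in affected subjects. The inputs below are assumptions, and all 200 subjects are taken as otherwise evaluable.

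Let a be the proportion with an adverse event, f1 their 24-month failure rate and f0 the rate in the others. With full follow-up the rate is a × f1 + (1 − a) × f0. If every affected subject leaves, the observed rate is f0.

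With f1 = 10% and f0 = 2%:

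- a = 10% (20 of 200): 0.10 × 10% + 0.90 × 2% = 2.8%, against 2.0% observed.
- a = 25% (50 of 200): 0.25 × 10% + 0.75 × 2% = 4.0%, against 2.0% observed.

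A second version takes f0 from the retrospective study in the Introduction. Its 96.7% maintained correction agrees with 59/61, so f0 = 2/61 = 3.3%. With f1 = RR × f0, where RR is the assumed relative risk of failure:

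| a | RR | Full follow-up | Observed |
|---|---|---|---|
| any | 1 | 3.3% | 3.3% |
| 10% | 3 | 3.9% | 3.3% |
| 20% | 3 | 4.6% | 3.3% |
| 20% | 5 | 5.9% | 3.3% |
| 30% | 5 | 7.2% | 3.3% |

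At RR = 1 only sample size is lost. Without any assumption on RR the possible range is wide: if 40 of 200 are removed and 5 of the 160 kept recur, the rate in all 200 lies between 5/200 = 2.5% and 45/200 = 22.5%.

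**The case against.** The strongest reply is that the sentence was never meant literally. It sits under the heading Investigator Decision, in a list of reasons that may apply, and the words about other reasons suggest that an adverse event is one ground on which the investigator decides. A literal rule would empty the study, and the provisions in Step 2 show sites what is expected. This stands as an account of intent. It does not remove the need for a correction, because the sentence is an operative instruction and the PP definitions attach a consequence to not following it.

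The PP consequence is also limited, and this stands. All main analyses are ITT. PP is used only if it differs considerably from ITT, and no output in the SAP list is labelled PP. Exclusion from PP cannot change any reported complication or re-operation rate.

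Three stronger conclusions are tempting, and the documents do not support them:

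- *That subjects with an adverse event will in practice be removed from the results.* Nothing shows that any site will apply the sentence literally, and those kept in remain in ITT.
- *That the SAP table of events leading to discontinuation would equal the table of all events.* An event first recorded at the 24-month visit cannot lead to discontinuation.
- *That the symptomatic non-unions suggested by the 1.6% background rate (200 × 0.016, about 3 subjects) would be lost.* If the non-union is itself the triggering event, it has already been observed, and SAP 7.3.1 counts related events up to the last visit. Only what happens afterwards is lost.

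**Conclusion.** Wrong as written: an internal contradiction. Protocol 4.2.5 makes any adverse event a mandatory trigger for leaving the study, while the endpoints, visit schedule and safety sections require subjects with complications to be followed to 24 months. If followed, the sentence costs the 24-month radiograph and later complications of those subjects, with no imputation. If not followed, it creates a listed major violation that can take them out of a conditional, supportive analysis set, on terms that differ between SAP 6.2.2 and SAP 7.1.2.

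A reader might infer from the illustration that the reported rates will be understated. That does not follow. The adverse-event rates, failure rates and relative risks are all assumed, the documents support no particular values, and the bias disappears if the risks are equal. The finding rests on the wording, not on these figures.

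**What to change.** 1. **Protocol 4.2.5.** Reconcile the Investigator Decision sentence with the 24-month follow-up sections, so that an adverse event alone does not end study follow-up and data collection unless the subject withdraws consent. Reconcile in the same way the item under Other that lists device or index-procedure failure as a reason for removal; otherwise the contradiction returns there. This concerns observation only and sets no rule for clinical care.
2. **Protocol 8.2.2 and 9.3; SAP 6.2.2 and 7.1.2.** Limit the withdrawal-criteria bullet so that having an adverse event does not by itself exclude a subject from PP. Align the discretionary wording in SAP 7.1.2 with the definition in SAP 6.2.2.
3. **Subjects already exited for an adverse event.** Collect later outcomes from medical records where consent allows.

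Cost: a short protocol and SAP wording amendment, and record review for any subjects under item 3. No visits are added, since they are already scheduled for every subject. Complication rates may look slightly less favourable.

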#### **Lost to Follow-up**

When contact with the subject has been lost without completing the final visit assessment, and every attempt to contact has failed, the subject will be considered lost to follow-up. Final documentation regarding all attempts to contact the subject requesting their return for the final visit should be documented.

#### **Withdrawal of Consent**

The subject withdraws consent for participation in the study. Any method of contact with the subject in which they state they no longer want to participate in the study specific activities constitutes withdrawal of consent. When possible the reason for withdrawal will be documented.

#### **Site Termination or Study Termination**

A site or study may be terminated. When this occurs all subjects at the site will be withdrawn and documented as early termination. Reasons for site or study termination may include, but are not limited to the following:

- Administrative Concerns (e.g., inadequate subject enrollment, Investigator/institution non-compliance, change of business strategy, etc.);
- Safety Issues, including those due to non-compliance, which substantially affect the risk to benefit ratio of the study subjects at a site or for the study as a whole;
- Regulatory Body Mandate(s).

#### **Other (which may include):**

- Protocol deviation, noncompliance or violation;
- Sponsor recommendation;
- Device/index procedure failure, including subjects who had a previously unidentified medical history finding that made treatment with the Lapiplasty® Mini-Incision™ System unfeasible;
- Death.

## **5.0 PROCEDURE**

### **5.1 General Description**

Individual centers and investigators will be selected based on their expertise and proficiency in the Lapiplasty® Procedure utilizing the Lapiplasty® Mini-Incision™ System.

The term index procedure refers only to the use of the Lapiplasty® Mini-Incision™ System during the Lapiplasty® Procedure. All concomitant procedures leading up to and after the Lapiplasty® Procedure and use of any TMC devices are considered concurrent procedures and are to be conducted under the discretion of the surgeon in accordance to the hospital's standard of care.

*Note: A recommended procedure is presented below. It is recognized that individual patient anatomic variation, surgical conditions, or surgeon preference may necessitate modifications to the outlined*

*procedures. Regardless, surgeons must adhere to all TMC device's instructions for use as outlined in the IFU. The Lapiplasty® Mini-Incision™ System will only be used by properly trained and qualified medical personnel in accordance with the Instructions for Use (IFU). Failure to properly follow instructions may result in improper functioning of the device(s). No non-Treace products are to be used for the procedures, unless deemed medically necessary by the PI.*

## **5.2 Lapiplasty® Procedure (Mini-Incision™ Approach) (Index Procedure)**

### **5.2.1 Key Surgical Steps**

#### **Mini Dorsal Incision**

Make a direct dorsal, 3.5cm (approximate) incision and release the 1st TMT joint with a sagittal saw and osteotome.

#### **Triplanar Correction**

Insert SpeedSeeker™ Instrument and apply Mini-Incision™ Positioner over the skin of 1st metatarsal to perform 3-plane correction.

#### **Precision Cuts**

Secure the Mini-Incision™ Cut Guide on the SpeedSeeker™ and make precision joint cuts with the correction held in place.

#### **Controlled Compression**

Apply the Lapiplasty® Compressor to bring the precision-cut joint surfaces together for controlled apposition of the arthrodesis site.

#### **Plate Application**

Utilize the Lapiplasty® Plate Holder to apply the locking plates dorsally and medially, securely positioning the PlantarPower™ Plate across the tension side of the joint.

#### **Multiplanar Fixation**

Low-profile Lapiplasty® Biplanar Plating is designed to provide multiplanar stability.

## **5.3 Post Index Procedure – Post-Operative Care and Weight-Bearing Instructions**

The appropriate post-operative care and the timing to return the subject to weight-bearing is at the discretion of the Investigator/Institutional SOC and takes into consideration the subject's ability to safely begin weight-bearing. However, for purposes of this study, subjects should be bearing weight in a CAM boot by 3 weeks post-operatively. Below is a recommended approach for a patient's post-operative care.

- Subject may be either bandaged, put in splint/cast or put in boot at the time of surgery. If subject is fitted with CAM boot at discharge, the subject should be provided instructions on how to begin protected weight-bearing (see bullet 5). *The type of post-operative surgical protection utilized will be recorded on the eCRF. If subject is allowed to begin protected weight-bearing (in boot) at*

*discharge, the date that the subject is allowed to start weight-bearing in the boot will be recorded on the eCRF.*

- Subject is instructed to remain off the operative foot as much as possible for the first few days post-op. This is to limit bleeding and swelling and to allow soft tissues to recover.
- Subject leaves the surgery facility with crutches, walker, rolling knee scooter or wheelchair. *The type of post-operative mobility aid utilized will be recorded on the eCRF.*
- At the first post-op visit (00-14 days), bandages are removed, and the subject can be allowed to shower. Subject may wear an athletic sock. No bandages or splints are needed. The subject should be reminded of post-op care of the foot/surgical site.
- At the first or second post-op visit (0-14 days or 14-21 days), if the subject has not already been fitted for a CAM boot at discharge, the subject is fitted with a CAM boot (low or high). Subject should be provided with instructions on how to begin protected weight-bearing in the CAM boot and acceptable activities:
  - Subject is instructed to put weight on foot as tolerate in the restrictive boot.
  - Subject is instructed not to roll forward onto the big toe and should remain on flat foot.
  - Subject is instructed to remove the CAM boot multiple times daily and perform range of motion exercises for ankle and foot.

**NOTE: The subject must be fitted with a CAM boot and allowed to start protected weight-bearing no later than 3 weeks post-operatively.** *The date that the subject is allowed to start weight-bearing in the boot will be recorded on the eCRF.*

*NOTE: If the subject is unable to start weight-bearing by 3 weeks, the reason for the delay in weight-bearing should be documented on the eCRF as a protocol deviation. The subject should be brought in for an **Unscheduled Visit (See Section 7.10)** when they are ready to begin protected weight-bearing in the boot.*

- At the first or second post-op visit (0-14 days or 14-21 days), compression socks may be provided to the patient. The start date and the stop date (approx. by the 4-month visit) of use of the compression sock will be recorded.
- At the 6-week post-op visit, if the subject is clinically stable, patient can transition from the boot to a shoe (running or another athletic shoe). *The date that the subject is allowed to start to WB in a shoe will be recorded on the eCRF.* The transition from boot to shoe may occur over a period of days/weeks, depending on patient healing and tolerance. Subject are instructed that they can walk normally but are not to stand on toes, run, jump or do any other high impact activity.
- At the 4-month post-op visit, subjects are allowed to begin low impact exercise if they are clinically stable. *The date that the subject is allowed to start full unrestricted activities (i.e., running and jumping) will be recorded on the eCRF.*

